6.4 Study procedures – HCV treatment

During HCV treatment and in the follow-up period, patients with HCV will undergo monitoring for treatment adherence and safety per Standard of Care. Laboratory parameters and imaging used as part of the study endpoints are listed below. See Appendix B Study Schedule.

Cholesterol measurements

Patients' total cholesterol and LDL cholesterol will be obtained at screening and week 72 for cardiac risk calculations.

Cardiac biomarker and systemic inflammation assessment

For all participants, labs will be drawn at screening, week 24, and week 72: high sensitivity CRP (hSCRP), high sensitivity TRP (hsTRP), soluble markers of inflammation (IFN- γ , TNF- α , IL-6, CXCL9, CXCL10, CXCL11) and activated and exhausted naïve and memory T cells (percent of CD8+ and CD4+ T-cells which are HLA-DR+, CD38+, Tim-3+, or PD-1+).

Cardiac MRI

A subset of patients will undergo cardiac MRI; up to 12 patients will be recruited from each of the three groups to undergo cardiac MRI at the NIH clinical center at Day -7 (interim visit) and week 72. Patients who are claustrophobic or cannot tolerate the MRI procedure will not be selected for this portion of the study. Cardiac MRI will be utilized to assess changes in myocardial injury, degree of post-contrast enhancement, T1 mapping, and the function of the myocardium. See Appendix C for more details.

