10.1 Return of Withdrawn/Removed Subjects

A participant who has withdrawn may not return to the study.

11 Remuneration Plan for Subjects

Participants will not be renumerated for receiving HCV treatment.

Participants will receive \$25 remuneration as gift cards at those visits where stored sample blood draws are completed. Those visits are Screening, week 24, and week 72. If additional visits are needed to obtain bloodwork or imaging, this additional visit would also warrant a \$25 remuneration. We will not exceed a maximum of 3 additional visits and will encourage combined visits.

Participants will receive \$100 remuneration as gift cards provided by UMB study staff whilst working as special volunteers at the NIH site when participants have an MRI. These visits are at the time of day -7 (interim visit) and week 72. [name], [name], [name], and [name], are UMB sub investigators who are also special volunteers at NIH and are fully credentialed and able to see research patients at the NIH. They are also authorized to obtain informed consent, provide remuneration to subjects visiting the NIH site, have access to identifiable data, see patients at NIH and participate in manuscript preparation/review.

12 Monitoring

As this is an observational study with intervention limited to laboratory and radiologic data collection, safety issues are not expected. The PI and the study team will conduct regular monitoring of safety and report to the IRB as specified in section 9.

13 Statistical Considerations

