13.1 Sample Size Justification and Power

The proposal primary outcome for cardiovascular risk is change in hsCRP. The primary hypothesis is that HCV eradication will result in at least a two-fold decrease from the baseline elevated hsCRP to 12 months post-functional cure in HCV-monoinfected and HIV/HCV-coinfected patients, respectively. Based on a previous study, mean hsCRP before starting IFN-therapy in HCV-monoinfected patients was 0.97 ± 0.11 mg/L compared to 0.07 ± 0.07 mg/L in healthy controls(23). Among SVR patients the median hsCRP at baseline was 0.64 mg/L and decreased to 0.25 mg/L after treatment. With a sample size of 30 patients in each group, we assume than 95% will achieve SVR with Zepatier (elbasvir/grazoprevir), resulting in a sample size of 28 patients in each group. In a paired t-test analysis (from baseline to 12-month post-treatment), with $\alpha=0.05$, power of 90% ($1-\beta$), and standard deviation (σ) = 0.15, we will be able to detect a true difference in the mean hsCRP response of matched pairs of 0.1 mg/L in each group or 0.8 mg/L with 80% power.

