13.2 Statistical Analysis

We will perform univariate analysis to describe the demographic and clinical characteristics of the study population. Count with percentages will be calculated for categorical variables and mean + standard deviation or median (interquartile range) for continuous variables. The independent variable is the three groups of participants with HCV, HIV/HCV, and HIV. Separate analysis will be done for each study group for the change in the primary outcome of HsCRP, from baseline to 18 months after baseline, in a paired t-test analysis, as well as for the secondary outcomes of cardiac biomarkers, MRI, and cellular and soluble immune markers of activation. Baseline comparison of hsCRP, cardio biomarkers, MRI, and cellular and soluble immune markers of activation between the three groups of participants will be performed using one-way or Kruskal-Wallis analysis of variance (ANOVA) for continuous variables and chi-square test of independence or Fisher's exact test for categorical variables. A linear regression model will be used in adjusted analysis for continuous dependent variables, while logistic regression model will be used in adjusted analysis for binary dependent variables. All analysis will be conducted in SAS, version 9.4 (SAS Institute, Inc., Cary, NC) with a P-value of less than 0.05 indicating statistical significance.

14 Ethics/Protection of Human Subjects

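### The primary paired t-test uses single, apparently untransformed hsCRP values with no rule for draws during acute illness, so one raised week-72 value can remove a group's power

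*Combined protocol and SAP*

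**What the plan says.** Section 13.1 names the endpoint: "The proposal primary outcome for cardiovascular risk is change in hsCRP". Section 6.4 (cardiac biomarker and systemic inflammation assessment) schedules it: "labs will be drawn at screening, week 24, and week 72: high sensitivity CRP (hSCRP". Appendix B shows the same three time points, with one draw at each. Week 24 is not part of the primary contrast.

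Section 13.2 analyses each group separately, "from baseline to 18 months after baseline, in a paired t-test analysis", "with a P-value of less than 0.05 indicating statistical significance". No transformation is stated. Section 13.1 sizes the test in mg/L: 95% SVR out of 30, "resulting in a sample size of 28 patients in each group", and, with a standard deviation of "0.15, we will be able to detect a true difference in the mean hsCRP response" of 0.1 mg/L at 90% power. The hypothesis in sections 3.4 and 13.1 is a ratio, at least a two-fold decrease.

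There is no deferral for acute illness, repeat draw, hsCRP ceiling, outlier rule, log analysis or paired rank test. Kruskal-Wallis appears only for the baseline comparison between groups, and the median with interquartile range only for description. Two provisions come close. Section 4.3 has a general investigator-discretion exclusion, which concerns eligibility and does not govern the week-72 draw. Section 11 pays for extra visits ("If additional visits are needed to obtain bloodwork or imaging"), up to three, but gives no trigger for repeating an hsCRP.

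**The concern.** hsCRP is a marker of systemic inflammation, and section 6.4 lists it under that title. A draw taken during an unrelated infection or injury therefore measures something other than the effect of HCV cure. The plan's SD of 0.15 mg/L leaves little room for such a value. In a raw-scale paired t-test with 28 pairs, one large difference moves the mean and inflates the standard error together, so the other 27 pairs may no longer be enough for significance.

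Without a rule, the team would either accept a result driven by one sample or decide what to do with it after seeing the data. The second is hard to defend in a non-randomised study with a single primary biomarker.

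**Working it through.** **Inputs from the documents.** Pairs n = 28, SD 0.15 mg/L, detectable difference 0.1 mg/L, baseline mean 0.97 mg/L, SVR medians 0.64 and 0.25 mg/L (all section 13.1); α = 0.05 (sections 13.1 and 13.2).

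**Assumptions.** Two-sided test; 0.15 read as the SD of the paired differences (the reading that reproduces the plan); raw scale, inferred from the mg/L sizing and the lack of a stated transformation; an excess X added to one participant's value.

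**1. The plan's own figure.** The noncentrality is 0.1 / (0.15/√28) = 3.53 and the critical t on 27 df is 2.05, so power is 92.5%. The difference detectable at 90% power is 0.095 mg/L, which rounds to the stated 0.1. (At 80% power it is 0.082, so the printed 0.8 looks like a slip for 0.08, a separate matter.)

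**2. Effects to test against.**
- Detectable difference: 0.1 mg/L.
- Cited fall in SVR patients: 0.64 − 0.25 = 0.39 mg/L.
- Two-fold fall from 0.97: 0.97/2 = 0.485 mg/L.

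**3. Effect of one raised week-72 value.** For a true fall d, the expected mean change is −d + X/28, the SD of the differences is about √(0.15² + X²/28), and t ≈ mean/(SD/√28). For X = 2 and d = 0.1 the mean is −0.1 + 0.071 = −0.029, the SD is 0.407 and t ≈ −0.37. As X grows, |t| tends to 1, below 2.05, whatever the other 27 pairs show.

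Simulated power for a significant decrease (40,000 trials per setting or more, differences Normal(−d, 0.15)), with X = 5 − 0.97 = 4.03 and X = 10 − 0.97 = 9.03:

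| True fall | No excess | X = 4.03: t ≈ | Power | X = 9.03: t ≈ | Power |
|---|---|---|---|---|---|
| 0.1 | 92.5% | +0.30 | 0% | +0.69 | 0% |
| 0.39 | about 100% | −1.68 | 4% | −0.21 | 0% |
| 0.485 | about 100% | −2.33 | 91% | −0.50 | 0% |

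At a fall of 0.1, X = 0.5 leaves 68%, X = 1 leaves 17% and X = 2 leaves 0%.

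The 91% is sensitive to how the excess is counted. X is added to a participant whose expected week-72 level is already 0.485. If the recorded value is exactly 5, the excess is 5 − 0.485 = 4.515, t ≈ −1.98, and simulated power is about 35%.

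**4. One raised baseline value.** At a true fall of 0.1, power is 68% at X = 2, 26% at X = 3 and 0.1% at X = 5. The estimated fall is exaggerated: 0.1 + 5/28 = 0.28 at X = 5. With no true change, a significant decrease occurs in 2.9%, 0.2% and 0% of trials at X = 1, 2 and 4, against a nominal 2.5%.

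**5. Alternatives.**
- Log scale: a value of 5 to 50 mg/L against 0.97 multiplies the geometric mean ratio by exp(ln(v/0.97)/28), which is 1.06 to 1.15.
- Under assumed lognormal data (medians 0.64 to 0.25, CV 0.5 to 1.5, correlation 0.5) and X = 10 at week 72, the log-scale paired t-test keeps 93% to 100% power and the raw-scale test 0% to 1%.
- Wilcoxon signed-rank at a fall of 0.1 and X = 10 to 50: about 77% (week 72) or 94% (baseline), against about 91% with no excess.

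**6. Frequency.** Each group has 28 × 2 = 56 primary draws. If 1%, 2% or 5% of draws fell in an acute illness (assumed), the chance of at least one is 1 − (1 − p)^56 = 43%, 68% or 94%.

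**The case against.** **The effect size.** The 0.1 mg/L is what the study can detect, not what it expects. The hypothesis is a two-fold fall, and a moderate spike is survivable there: at X = 4.03 power is still about 91%. This stands, and it limits the claim. It does not help at values of 10 mg/L or more.

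**Outside inputs.** Neither the size nor the frequency of illness-level values is in the documents, and the groups are tested separately, so one value affects one group's test. This also stands. The calculation shows how fragile the test is, not how likely failure is.

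**The scale is the main driver.** Most of the loss comes from using the raw scale, and a log analysis recovers most of it without any draw rule. The size of the loss also depends on the SD of 0.15: with an SD of 1.0 and a fall of 0.39, power is only 51% before any spike. This is why the fix puts the scale first and treats the draw rule as a supplement.

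**A stronger reading to avoid.** A reader might infer that a spike at baseline would create a false finding of benefit. The calculation does not support that. The estimated fall is exaggerated, but the SD rises with it and the false-positive rate stays near or below nominal. Nor can one infer that the primary test will fail even if cure works, because that depends on values and frequencies that the documents do not give.

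**Conclusion.** The concern holds as a weakness in robustness. The stated test has no protection against one aberrant hsCRP value, and the plan has no rule to prevent or handle one. An excess of 2 mg/L or more in one of 28 week-72 values takes power at the detectable difference from 92.5% to about 0%. At the cited 0.39 mg/L fall an excess of about 4 mg/L is enough. At a two-fold fall from 0.97 the same excess leaves most of the power, and a value of 10 mg/L leaves none.

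This rests on the raw-scale reading of section 13.2, on 0.15 as the SD of paired differences, and on assumed illness-level values. The study is a pilot and the remedy is cheap, so the change should be made, but the point does not invalidate the design.

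**What to change.** **Section 13.2.** Make the primary test a paired t-test on the log ratio of week-72 to baseline hsCRP within each group, reported as a geometric mean ratio with its confidence interval. This matches the two-fold hypothesis in section 3.4. Prespecify a Wilcoxon signed-rank test as the sensitivity analysis. Do not exclude pairs above an hsCRP cut-off: that selects on the outcome and would also drop genuinely high values.

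**Section 6.4.** Add a prespecified rule, identical at both visits and in all three groups, to defer or repeat the research hsCRP draw when the participant reports a recent acute illness. Define the look-back window before data are seen. Section 11 already allows up to three additional paid visits, though it does not say that repeat assays are funded.

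**Cost.** A few repeat draws and assays, one question per visit, and an effect reported as a ratio instead of in mg/L. The log analysis does not remove all sensitivity: under the widest assumed spread (CV 1.5) and an excess of 50 mg/L at week 72 it keeps about 80% power, so the draw rule still has a use.

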6.4.1 Stored sample collection

Blood samples for storage and research will be obtained at screening (total of 11 tsp), and at weeks 24 and 72 (a total of 9 ½ tsp). Samples collected will include:

- Serum storage (10 mL) SST/tiger top (2 teaspoons)
- Plasma storage (6ml) EDTA (1 teaspoon)
- DNA paxgene will be collected (8.5ml) one time at baseline (1 ½ teaspoon)
- RNA paxgene will be collected (2.5ml) (1/2 teaspoon)

- Peripheral blood mononuclear cells (30 ml) Green top/heparin (6 teaspoons)

6.4.2 HIV and HCV monitoring

HCV RNA will be checked per standard of care. HIV VL and CD4 will be checked per standard of care for HIV mono- and co-infected patients. HIV antibody/antigen will be checked at screening for those who are HCV mono-infected.

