6.3 Standard of care HCV treatment

All participants with HCV will be started on HCV treatment on Day 0 after confirming eligibility. Patients will complete visits and laboratory monitoring as per standard of care guidelines.

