6.4.3 Viral sequencing

Individuals with new seroconversion to HIV will have sample sent for viral sequencing and phylogenetic analysis. Individuals with detectable HCV RNA after completion of HCV treatment or new infection during the follow up period will have current sample, and baseline stored sample sent for viral sequencing and phylogenetic analysis.

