6.4.4 Linkage to care

Any participant who seroconverts to HIV+ will be immediately linked to care, in DC or in Baltimore.

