7.2 Potential Benefits

Subjects may be cured of hepatitis C during the course of this study. Also, they will contribute to the body of scientific research on treatment of hepatitis C and cardiovascular risk in people with living with HIV and/or HCV. Furthermore, by achieving functional cure of HCV, subjects will no longer be a potential source of HCV transmission in the community. It is possible that subjects will receive no benefit from the study participation.

8 Stored Samples and Future Research

We will study the viral and host immunity to HCV and HIV in all patients. The results will be used to characterize each individual with regards to immune status and chronicity of disease. Studies on research samples may include the following:

- A] HCV genome sequencing may be performed on plasma using the protocol as described and compared for variability and relatedness of sequences.
- B] We will screen sera from all patients for differential expression of protein using multiplex cytokine arrays, which has the capability of detecting several different cytokines and other biologically relevant proteins.
- C] We will perform detailed phenotypic and functional evaluation of immune cell types in the periphery. This will help us in determining the nature of antiviral immune responses in patients who are chronically infected, achieve SVR and acquire new HCV and HIV infections. Determination of specific immune defects in these individuals are important milestones in deciding future therapeutics and protective immunity to reinfection. Exhaustion and activation markers on T, B and NK cells will be quantified. Specific immune responses against pooled HCV peptides will be performed using an ELISPOT assay and/or flow cytometry.

Future use of the specimens will be based on the scientific merit of the investigation and would be decided by the Principal Investigator. They would be related to the study of HCV and/or HIV. Other investigators may wish to study these samples and/or data. In that case, IRB approval must be sought prior to any sharing of samples and/or data. Any clinical information shared about the sample would similarly require prior IRB approval. If approved, and once a Material Transfer Agreement (MTA) has been established, the study team may send de-identified samples to the collaborators. Investigators will use stored samples only for research.

8.1 Intended Use:

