APPENDIX B: Study Procedures Table

					M6	M18
HCV Treatment	Screening	Interim visit (Day -7)	Day 0	End of Treatment	Week 24	Week 72
Provider Visit	X^		X	X	X	
HCV SOC Labwork	X			X	X	
HCV RNA	X			X	X	X
HCV Ab	X^					^
HIV 4 th gen Ag/Ab	X					
HIV SOC Labwork	^					
HBV DNA (for HBcAb positive)	X^					
Total Cholesterol and HDL Cholesterol	X^					X^
Fibroscan or Fibrosure	X^				X^	
hsCRP, hsTRP	X^				X^	X^
Markers of inflammation	X^				X^	X^
Memory T cells	X^				X^	X^
Cardiac MRI		X^				X^
Urine Drug Screen	X^					

X= HCV mono- and HIV/HCV co-infected

^= HIV mono-infected

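### HCV mono-infected participants have no scheduled HIV test after screening, so the seroconversion provisions rely on off-schedule testing and an undetected new infection would stay in Group 1 at week 72

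*Combined protocol and SAP*

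**What the plan says.** Testing for HIV:

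- Section 6.4.2, for Group 1: "HIV antibody/antigen will be checked at screening for those who are HCV mono-infected". No later test is named. The continuing HIV monitoring in that section covers only people already known to be positive: "HIV VL and CD4 will be checked per standard of care for HIV mono- and co-infected patients".
- Appendix B: the row "HIV 4 th gen Ag/Ab" has one mark, at screening. It has none at Day 0, end of treatment, week 24 or week 72.

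Provisions that need a new HIV infection to be known:

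- Section 6.4.3: "Individuals with new seroconversion to HIV will have sample sent for viral sequencing and phylogenetic analysis".
- Section 6.4.4: "Any participant who seroconverts to HIV+ will be immediately linked to care, in DC or in Baltimore".
- Section 8 plans immune studies that include patients who "achieve SVR and acquire new HCV and HIV infections".

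Related provisions:

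- Appendix B repeats HCV antibody at week 72 in the HIV mono-infected group.
- Section 6.3 describes routine monitoring in general terms only: "Patients will complete visits and laboratory monitoring as per standard of care guidelines".
- Section 6.4.1: "Blood samples for storage and research will be obtained at screening (total of 11 tsp), and at weeks 24 and 72". No HIV test on the stored blood is planned.
- Section 13.2 analyses each study group separately and does not mention a change in HIV status.

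**The concern.** Groups 2 and 3 are HIV-positive at entry, so Group 1 is the only group in which HIV seroconversion can occur. It is also the group with no scheduled HIV test after entry. A rule that promises immediate linkage to care has no scheduled result to act on for about 18 months.

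The event is plausible in this population. Section 6 lists a drug treatment center among the study sites, and exclusion criterion 14 leaves entry after a positive drug screen to the investigator.

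HIV status also defines the comparison. Group 1 is the only HIV-negative group, and exploratory objective 3 looks at markers and MRI in HIV-positive and HIV-negative subjects. The Précis says that HIV produces persistent inflammation and immune activation, which hsCRP, the cytokines and the T-cell markers are meant to measure. An unrecognised new infection would place HIV-related inflammation in the HIV-negative group and would tend to hide a fall after HCV cure.

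**Working it through.** **1. The schedule.** Section 6.4.2 and Appendix B agree on one test, at screening. Set beside 6.4.3, 6.4.4 and section 8, no scheduled procedure supplies the result that those three provisions need. The untested period is 72 weeks from Day 0, plus the time from screening to Day 0. Section 6.1 lets outside labs from the last 6 months establish eligibility. If that covers the HIV test, the period could reach about 72 + 26 = 98 weeks.

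**2. How many cases.** With all 30 Group 1 participants followed to week 72 (no dropout), exposure is 30 × 72/52 = 41.5 person-years. The documents give no HIV incidence, so the rates below are assumptions. For rate r per person-year, p = 1 − exp(−r × 72/52), the expected number is 30p, and the chance of at least one is 1 − (1 − p)^30.

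| Assumed rate per 100 person-years | Expected infections | Chance of at least one |
|---|---|---|
| 0.1 | 0.04 | 4% |
| 0.5 | 0.21 | 19% |
| 1 | 0.41 | 34% |
| 2 | 0.82 | 56% |
| 5 | 2.0 | 87% |

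The range is too wide to size the problem. The gap in the schedule does not depend on it.

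**3. Effect on the primary analysis.** Inputs from section 13.1: n = 28 per group, SD 0.15 mg/L, α = 0.05 (two-sided assumed), paired t-test. Power comes from the noncentral t distribution with n − 1 degrees of freedom and noncentrality (d/SD) × √n.

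- The plan's own figure: the detectable difference at 90% power is 0.095 mg/L, which rounds to the stated 0.1. At d = 0.1 the noncentrality is (0.1/0.15) × √28 = 3.53 and power is 92.5%.
- Affected participants excluded: one (n = 27) gives 91.5%; two (n = 26) gives 90.4%.
- Affected participants kept, assuming no hsCRP change in them and SD still 0.15: one gives a mean of 0.1 × 27/28 = 0.0964 and power 90.6%; two give 0.1 × 26/28 = 0.0929 and power 88.4%.

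One unchanged participant dilutes the mean fall by 1/28 = 3.6%. If that participant's hsCRP rose by δ, the mean fall would be (27 × 0.1 − δ)/28, so a large rise would cost more than shown here.

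**4. Effect on the MRI subset.** Sections 6.2 and 6.4 allow up to 12 per group, so one misclassified participant could be 1/12 = 8.3% of the HIV-negative scans. The documents give no SD for MRI or immune markers, so no power effect can be computed.

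**The case against.** Sections 6.4.3 and 6.4.4 are conditional: they say what happens once seroconversion is known and do not promise surveillance. Participants attend clinics that provide HIV care, provider visits are marked at Day 0, end of treatment and week 24, and routine monitoring neither names nor excludes HIV re-testing. This stands against a stronger reading that a reader might infer, namely that the provisions can never be triggered. Routine testing could trigger them, and stored blood could reveal a case later, though too late for immediate linkage. What remains is that the study itself schedules nothing to find a case.

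A reader might also infer that the plan directs every seroconverter to be analysed as HCV mono-infected. It does not. That outcome follows only for undetected cases; for detected ones 13.2 is silent.

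The repeated HCV RNA tests in Groups 1 and 2 are not evidence of uneven surveillance, because they are needed to establish cure. Only the week-72 HCV antibody test in Group 3 is a fair comparison.

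On cost, stored research blood is not a ready substitute. Section 8.5 says that its results generally do not go to the primary care provider or the medical record, and Appendix B marks no provider visit at week 72. But clinical blood is already due then: Appendix B marks HCV RNA for Groups 1 and 2 at weeks 24 and 72. The need for a route to return results stands.

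**Conclusion.** The gap is real and is visible from the text alone. Group 1 has no scheduled HIV test after screening, three provisions presuppose that new infections become known, and 13.2 has no rule for them. An undetected seroconverter would be analysed at week 72 as HCV mono-infected.

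Its size is uncertain. The number of cases cannot be estimated from the documents. The documents do not support a claim of serious damage to the primary result: with one affected participant showing no change, power at 0.1 mg/L stays near 90%, given n = 28 and SD 0.15. The case for acting rests on participant safety, on consistency between the schedule and the seroconversion provisions, and on the immune and MRI comparisons that use HIV status, where MRI has at most 12 per group.

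**What to change.** - Reconcile 6.4.2 and Appendix B with 6.4.3 and 6.4.4: add HIV 4th-generation Ag/Ab for Group 1 to the clinical draws already scheduled at weeks 24 and 72. Each later hsCRP value then has an HIV test from the same visit.
- State the route by which a result reaches the participant, in particular at week 72, where no provider visit is marked.
- In 13.2, flag any participant who seroconverts and add a sensitivity analysis of the Group 1 change that excludes that participant's values after infection. State how infection is dated from the last negative and first positive tests.

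The cost is up to 30 × 2 = 60 routine assays, the work of returning results, and short edits to 6.4.2, Appendix B, 13.2 and the consent form. The blood draws are already planned; whether week 72 needs an added contact depends on the result-return route chosen.
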